3 STUDY IMPLEMENTATION

3.1 STUDY DESIGN

This protocol is a single-arm design and will implement CALM therapy in PCNST patients currently enrolled in the NIH trial 16C0151. Study enrollment, treatment, and all study procedures will be done remotely. Only ISSO approved telehealth platforms will be utilized for telehealth procedures.

All telehealth/remote procedures used in this protocol will be consistent with applicable NIH policies (e.g., Medical Administrative Series policy, M20-1 found at: <https://cc-internal2.cc.nih.gov/policies/PDF/M20-1.pdf>).

Because our outcome measures (depression, distress, quality of life) are affected by recurrence, we will try to enroll an adequate representation of participants with recurrence and no recurrence.

Participants will be assigned to a CALM therapist and complete baseline questionnaires before starting CALM therapy. Prior to the completion of each session, future sessions will be scheduled with the participant.

CALM includes 3-6 individual therapy sessions, each approximately 45-60 minutes in length, delivered over 6 months. Additional sessions may be offered if clinically indicated while the participant is on the study, with the CALM domains being revisited if the participant is still experiencing challenges and the CALM therapist identifies this need to help the participant process any additional feelings. A maximum of 3 booster sessions will be offered. These additional sessions may be offered if clinically indicated while the participant is on the study.

Prior to each session, CALM therapist will confirm that participant is at home address on file and will have the contact information for a patient identified contact (either living in the home or primary contact outside of the home) and local provider. If the participant is showing signs of being in danger to themselves or others, the participant's location will be confirmed, the patients contact (living in the home or outside) will be contacted by phone and a brief safety plan (identify coping strategies, provide professional emergency contacts) will be created to minimize risk of harm. The CALM therapist will stay in contact with the participant until identified contact or healthcare provider has been reached and they can continue on with management of the participant's care. The information collected from the participant (location, if identified contact is in the home or not) will be provided to the health care provider identified by the participant.

All sessions will be audio-recorded. Sessions will be recorded for treatment integrity and quality assurance, with therapists getting supervision from [name] (also an investigator on this study) from Princess Margaret (recordings will be reviewed on a select number of recordings), it will be a way to make sure the CALM intervention is being conducted effectively, that the domains are being targeted and therapists can be evaluated to assess their abilities and improve any areas in the therapeutic relationship. Participants can request that their session not be recorded, and they will still be able to participate in the study. If information is shared during the sessions that the study participant needs continued psychological interventions, the participant's healthcare team will be notified so that appropriate referrals can be made.

CALM includes 4 interrelated domains that will be covered during sessions.

- Symptom management and communication with health care providers
- Changes in self and relations with close others
- Sense of meaning and purpose
- The future and mortality

All modules will be addressed with each participant, but the sequencing and time devoted to each domain will vary, based on the concerns that are most relevant to each participant.

Therapists involved in this study will be health care professionals involved in the care of primary central nervous system tumor participants and able to deliver psychotherapy. CALM therapists are deemed competent in delivering CALM after attending a minimum of one CALM training workshop and following successful completion of 2 training cases (e.g., completion of 3-6 sessions per participant, under supervision), whereby the therapist-in-training sufficiently demonstrates competence in CALM, as judged by the intervention developers or other certified CALM trainers. Supervision from the PM staff will require use of 2 questionnaires.

- The CALM: Evaluation of Therapists Competencies instruments will be used to evaluate CALM therapists to identify adherence to the CALM intervention and to further develop therapist skills during supervision. Both documents will be used by the PM team when supervising the NOB CALM therapists.

Participants will be asked to complete additional questionnaires approximately at 3 and 6 months.

Family caregivers (e.g., spouse, adult son/daughter, family member, or other persons accompanying the participant) of participants involved in the study may be invited to participate in at least one CALM session with the participant. However, caregivers are not required to participate.

Qualitative interviews will be conducted on select participants after their 3rd session to evaluate how participants experienced or evaluated (a) the overall CALM therapy; (b) each of the four CALM dimensions; (c) the therapeutic alliance, and (d) the structure and timeframe of CALM. Caregivers may be invited to complete a qualitative interview with the participant. However, caregivers are not required to participate.

Once participants have completed their therapy sessions and finished their last set of questionnaires, they will be taken off study (see Off-Study Criteria Section [3.6](#)).

3.2 OUTCOMES QUESTIONNAIRES

Outcome measures will be completed by participants at time points indicated in Study Calendar [3.4](#) to coincide with CALM intervention session time points and take approximately 40-60 minutes to complete.

These instruments are described in Section [1.2.3](#), submitted as a separate document, and will include the following:

- The Patient-Reported Outcomes Measurement Information System (PROMIS-Depression)
- The Death and Dying Distress Scale (DADDS)
- The Quality of Life-Cancer Scale (QUAL-EC)
- The modified and brief Experiences in Close Relationships (ECR-M-16)
- Presence and severity of the symptoms (MDASI-BT or MDASI-SP)
- Health outcomes (EQ-5D)
- The Clinical Evaluation Questionnaire (CEQ)*

- The Was it Worth it Questionnaire (WIWI)*

***NOTE:** All Outcomes questionnaires will be completed at baseline, 3-month, and 6-month timepoints, except for the CEQ and WIWI which will be completed at the 3-month timepoint and if more than 3 sessions are completed, the CEQ and WIWI will also be completed at the 6-month timepoint.

A survey link will be sent out to participants for completion of study questionnaires at all time points.

The questionnaire responses will be entered by study subjects directly into the Scribe/Labmatrix system.

Those participants who do not return an assessment within 2 weeks may receive up to 2 reminder email/telephone calls from research staff.

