1.2.2 CALM Psychotherapy

CALM is a semi-structured, manualized, individual psychotherapy designed for patients with advanced cancer and their loved ones. It shares features with manualized supportive-expressive (30, 39-43), cognitive-existential (44, 45), and meaning-centered (46) group psychotherapies applied to patients with advanced and terminal disease. It was developed based on empirical data, clinical observations, and the theoretical foundations of relational (47), attachment (48), and existential (49) theory. It is informed by Princess Margaret's team CIHR-funded longitudinal research aimed at identifying the antecedents and course of psychosocial morbidity in individuals with metastatic cancer (16-19, 21, 50).

CALM includes 3-6 individual therapy sessions, each approximately 45-60 minutes in length, delivered over 3-6 months. Additional sessions may be offered if clinically indicated while the participant is on the study, with the CALM domains being revisited if the participant is still experiencing challenges and the CALM therapist identifies this need to help the participant process any additional feelings. A maximum of 3 booster sessions will be offered. The sessions cover 4 domains: 1) symptom management and communication with health care providers; 2) changes in self and relations with close others; 3) sense of meaning and purpose, and 4) the future and mortality (38). CALM will be done following the manual that was created by the researchers at Princess Margaret (PM), which is currently in print (51). All modules will be addressed with each patient, but the sequencing and time devoted to each domain will vary, based on the concerns that are most relevant to each patient. The patient's caregiver (e.g., spouse, adult son/daughter, family member), or other persons accompanying the patient are encouraged to participate in one or more of the therapy sessions, as deemed appropriate by the patient and therapist. CALM can be delivered by specially trained therapists from a wide range of disciplines, including social work, nursing, psychiatry, psychology, and medicine (38, 52).

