2 ELIGIBILITY ASSESSMENT AND ENROLLMENT

2.1 ELIGIBILITY CRITERIA

2.1.1 Inclusion Criteria

- Subjects with histological or imaging confirmation of PCNST who are undergoing standard of care or experimental treatment.
- Adults (≥ 18 years of age) who are English-speaking
- Subjects who have a life expectancy of at least 3 months from time of study entry to allow for participation in the 3 required sessions.
- Subjects must be enrolled on the Neuro-Oncology Branch Natural History Study 16C0151.
- The ability of the subject to understand and the willingness to sign a written informed consent document as determined by the assessment of the treating physicians.

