3.4 STUDY CALENDAR

Procedure	Baseline evaluation	CALM Therapy	3-month evaluation (+/- 2 weeks)	6-month evaluation (+/- 2 weeks)
CALM Therapy ¹			→	
Adverse Events			→	
PROMIS-Depression	X		X	X
The Quality of Life at the End of Life-Cancer Scale (QUAL-EC)	X		X	X
The Death and Dying Distress Scale (DADDS)	X		X	X
Experiences in Close Relationships (ECR-M-16)	X		X	X
Clinical Evaluation Questionnaire (CEQ) ⁵			X	X
MDASI-BT or MDASI-SP ²	X		X	
EQ-5D ²	X		X	
Qualitative Interview ^{3,4}		X		
WIWI ⁵			X	X

1. CALM therapy includes 3-6 individual sessions delivered over 6 months. Additional sessions may be offered if clinically indicated while the participant is on the study.
2. Completed within 2 months prior to CALM therapy and any time after the 3rd CALM session while the participant is on the study. If these questionnaires are completed on 16C0151 protocol within the time frames required by this protocol, completion of these questionnaires do not need to be repeated.
3. The Qualitative Interviews will be conducted and scheduled within 1-2 months after participants' 3rd session.
4. The Qualitative Interviews will be conducted on a select number of participants until data saturation is reached (i.e., estimated to be 15-30 patients).
5. The CEQ and WIWI will be completed at 3 months with 6 month completion if more than 3 sessions are completed.

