8.3.2 Analysis of the Secondary Endpoints

This study will report feasibility metrics associated with the implementation of CALM remotely in a primary central nervous system tumor population, including compliance, eligibility, accrual, adverse effects, study completion, and participant satisfaction with the intervention. If attrition is less than 20% of enrolled participants, this study is considered feasible. If 50% of participants report satisfaction with the intervention on the WIWI it will be considered feasible.

To describe the effects of the CALM intervention on death anxiety we will calculate total scores, subscale scores, and/or t-scores (if applicable) for the Death and Dying Distress completed at varying time points (baseline, month 3, and month 6). This data will be summarized by time point quantitatively and graphically. To quantify the immediate CALM effect, we will calculate the effect size difference between baseline scores and month 3. To quantify the long-term CALM effect, we will calculate the effect size differences between baseline and month 6.

Previous data on death anxiety reported by advanced cancer participants who underwent CALM showed a reduction of 8 (SD of the difference=15.7). With 80 participants, we have 99% power to detect this difference using a two-tailed test at a 5% significance level. To determine whether there is sufficient power to demonstrate reductions in psychological distress and psychological well-being, we need preliminary data on these variables that is due to the CALM treatment. In the absence of preliminary data, we cannot provide statements about the statistical power of these secondary endpoints. However, this study will generate preliminary data that will inform future studies.

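### A participant whose third and last CALM session falls after the month-3 WIWI and CEQ rates an unfinished course and is not asked again

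*Combined protocol and SAP*

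**What the plan says.** Section 3.2 gives the CEQ and WIWI at month 3 and then says "if more than 3 sessions are completed, the CEQ and WIWI will also be completed at the 6-month timepoint". Footnote 5 of the calendar in section 3.4 states the same rule: "The CEQ and WIWI will be completed at 3 months with 6 month completion if more than 3 sessions are completed". The calendar sets the month-3 evaluation by date, with a margin of 2 weeks either side, and not by session count.

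Section 3.1 describes delivery as follows: "CALM includes 3-6 individual therapy sessions, each approximately 45-60 minutes in length, delivered over 6 months". Calendar footnote 1 agrees: "CALM therapy includes 3-6 individual sessions delivered over 6 months". The background in section 1.2.2 differs slightly: "CALM includes 3-6 individual therapy sessions, each approximately 45-60 minutes in length, delivered over 3-6 months". The required course is three sessions. Section 2.1.1 asks for a "life expectancy of at least 3 months from time of study entry to allow for participation in the 3 required sessions".

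Other assessments made after the course use a different anchor. Calendar footnote 2 places MDASI and EQ-5D follow-up after the third session, and section 3.3 and footnote 3 place the interview 1-2 months after it. Section 3.2 also says in general terms that questionnaire timing is meant to match the sessions.

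The WIWI carries a decision. Section 8.3.2 states: "If 50% of participants report satisfaction with the intervention on the WIWI it will be considered feasible". It names no timepoint for that rule, applies the same percentages at the interim analysis, and uses the WIWI to assess tolerability and acceptability.

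**The concern.** The repeat at month 6 depends on how many sessions a participant has had, not on whether the required course was finished when the first form was answered. Someone who completes four sessions before month 3 is asked twice. Someone whose third and final session falls in month 4, 5 or 6 is asked once, before that session.

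The WIWI and CEQ ask participants to judge the intervention and the therapist's support. Section 3.1 says that all four domains are covered but in an order that varies by participant, so an early form may precede some of them. For late finishers with exactly three sessions, the plan holds no questionnaire rating of the completed course. At stake is what the 50% satisfaction criterion measures: a mix of finished and unfinished courses, in proportions that the plan does not ask to be reported.

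**Working it through.** **Inputs.** The form rule comes from section 3.2 and calendar footnote 5, the month-3 window from section 3.4, and the delivery period from sections 3.1, 3.4 and 1.2.2. The 50% rule comes from section 8.3.2. The respondent number comes from section 8.2, which plans 80 evaluable of 100 enrolled.

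**The plan's own figure.** Section 8.2 assumes a mean reduction of 1.8, an SD of the difference of 5.7, two-sided 5% and 80% power. The normal approximation gives ((1.960 + 0.842) × 5.7 / 1.8)² = 78.7, so 79. The exact paired t calculation gives 81, and power at 80 is 79.7%. With 20% attrition, 80 / 0.8 = 100. The stated 80 and 100 are reproduced. They serve here only as a denominator, and nothing in this point changes sample size, alpha or power.

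**What the rule does to permitted schedules.** The month-3 window closes at 3 + 14/30.4 = 3.46 months. The schedules below are illustrations; the documents prescribe none of them.

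| Sessions | Session months | Done when the window closes | WIWI/CEQ at month 6? |
|---|---|---|---|
| 3 | 1, 2, 3 | 3 | no, and the month-3 form can follow the whole course |
| 3 | 0, 3, 6 | 2 | no |
| 3 | 2, 4, 6 | 1 | no |
| 4 | 0, 2, 4, 6 | 2 | yes |
| 4 | 1.5, 3, 4.5, 6 | 2 | yes |
| 6 | 1, 2, 3, 4, 5, 6 | 3 | yes |

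The gap is confined to rows two and three: session 3 after the window and no fourth session. Section 1.2.2 also has an upper limit of 6 months, so the gap exists under either statement of the delivery period. The documents do not say whether month 3 runs from baseline or from the first session. Section 2.4 puts most baseline measures within 14 days before therapy, so this could move the window by up to 2 weeks and does not remove the gap.

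**How many, and what it could do to the 50% rule.** The share affected is not in the documents. Take s = 10%, 20% or 30% of 80 as an assumption, so k = 80s. The 50% rule is met at 40 of 80. Suppose exactly 40 report satisfaction and the k early raters are split evenly. If all k could answer differently after the course, the satisfied count lies between 40 − k/2 and 40 + k/2.

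| Assumed share | k | Satisfied count | Possible satisfaction after the course |
|---|---|---|---|
| 10% | 8 | 36 to 44 | 45% to 55% |
| 20% | 16 | 32 to 48 | 40% to 60% |
| 30% | 24 | 28 to 52 | 35% to 65% |

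These are outer limits, not expected shifts. With 100 respondents the percentages are the same (k = 10, 20, 30). If the early raters had all answered the same way, the largest shift would be k/80, that is 10, 20 or 30 percentage points in one direction. The further the observed result lies from 50%, the less this timing gap can change the decision.

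**The case against.** The strongest reply is that the plan expects three sessions in about three months, so the month-3 form follows the required course and the month-6 form follows any further sessions. Several sections support this. The life-expectancy criterion ties 3 months to the three required sessions. Section 1.2.2 gives 3 months as the lower end of delivery. Section 3.1 books future sessions before the current one ends, and section 3.6.1 has missed sessions rescheduled within 14 days. This stands as a reason to think that the affected group may be small. It does not close the gap, because none of these provisions sets a deadline for session 3 or holds the form until it has happened.

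A second reply is that a fixed month-3 form captures people who die or leave before month 6. That also stands, and is a reason to keep the form.

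A third is that interviews after session 3 supply satisfaction data. They cover an estimated 15-30 selected participants and do not enter the 50% rule.

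A reader might go further than the documents allow in three ways.

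- One might infer that every slower participant is lost to later rating. Those who reach four or more sessions are asked again.
- One might infer that month-6 raters are more engaged, so that satisfaction is inflated. Section 3.1 links additional sessions to continuing difficulty, so the group could equally be more distressed. It is selected, but the direction is unknown.
- One might infer that no WIWI result describes satisfaction with CALM. For everyone with three sessions done by the month-3 form, it rates the required course.

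**Conclusion.** The gap is real and narrow. Followed as written, sections 3.2 and 3.4 leave a participant whose third and last session comes after the month-3 window with no WIWI or CEQ on the completed course. This is out of step with the session-3 anchor used for MDASI, EQ-5D and the interviews. The range of 8-24 ratings out of 80 rests wholly on an assumed share of 10-30% and is not an estimate of the number affected. The consequence is limited to the 50% satisfaction rule, at the interim and at the end, and to the reading of tolerability and acceptability. It matters to the rule only if observed satisfaction is near 50%. No decision rule uses the CEQ, so for that form the loss is descriptive. The primary endpoint is untouched. The change is still worth making, because it is cheap and lets the criterion rest, where possible, on the course that each participant received.

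**What to change.** In section 3.2 and calendar footnote 5, keep the month-3 form. Also give the WIWI and CEQ at month 6 to every participant who had not completed session 3 when the month-3 form was answered. It would be simpler to give them to all participants still on study at month 6.

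In section 8.3.2, base the 50% criterion on each participant's last WIWI. Report the number of sessions completed at that form, and show the month-3 result alongside. This also supplies the timepoint that the rule now lacks.

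The delivery period in section 1.2.2 and that in sections 3.1 and 3.4 should be reconciled by the sponsor. This change concerns questionnaire timing only and does not depend on which is kept.

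The cost is wording in three places, plus four yes/no items and the CEQ in a month-6 survey that participants already receive by link. An extra form tied to session 3 would also work but needs its own mailing. One limit remains: participants lost before month 6 still contribute an early rating, which the reported session count makes visible.

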3.3 CALM QUALITATIVE INTERVIEW

One qualitative interview will be completed by a select number of participants (within 1-2 months) after completion of the 3rd CALM session. The time to complete the interview is approximately 15-20 minutes. Interviews will be conducted until thematic saturation is reached (i.e., adequate data has been identified and no new information is expected). Thematic saturation is estimated to be between 15-30 participants. The research team will assign the interviews to the first 15 participants starting with enrollee #5. This group of 15 will be evaluated and additional participants will be selected if saturation has not been reached.

All qualitative interviews will be audio-recorded and transcribed. Transcripts (i.e., with names, any clearly identifying information, and site-specific medical record numbers, if mentioned, will be deleted from the transcripts) will be filed according to participants' ID and also securely stored in secure servers in the Neuro-Oncology branch.

This instrument is submitted as a separate document.

3.4 STUDY CALENDAR

Procedure	Baseline evaluation	CALM Therapy	3-month evaluation (+/- 2 weeks)	6-month evaluation (+/- 2 weeks)
CALM Therapy ¹			→	
Adverse Events			→	
PROMIS-Depression	X		X	X
The Quality of Life at the End of Life-Cancer Scale (QUAL-EC)	X		X	X
The Death and Dying Distress Scale (DADDS)	X		X	X
Experiences in Close Relationships (ECR-M-16)	X		X	X
Clinical Evaluation Questionnaire (CEQ) ⁵			X	X
MDASI-BT or MDASI-SP ²	X		X	
EQ-5D ²	X		X	
Qualitative Interview ^{3,4}		X		
WIWI ⁵			X	X

1. CALM therapy includes 3-6 individual sessions delivered over 6 months. Additional sessions may be offered if clinically indicated while the participant is on the study.
2. Completed within 2 months prior to CALM therapy and any time after the 3rd CALM session while the participant is on the study. If these questionnaires are completed on 16C0151 protocol within the time frames required by this protocol, completion of these questionnaires do not need to be repeated.
3. The Qualitative Interviews will be conducted and scheduled within 1-2 months after participants' 3rd session.
4. The Qualitative Interviews will be conducted on a select number of participants until data saturation is reached (i.e., estimated to be 15-30 patients).
5. The CEQ and WIWI will be completed at 3 months with 6 month completion if more than 3 sessions are completed.

